9.1.3. Informed Consent Procedure

Informed consent must be obtained prior to subject enrolment in the study (as described in Section 14.1.3) and before any protocol-directed procedures are initiated. A unique subject identification number (subject ID = site number + subject number) will be assigned to each subject at the time that informed consent is obtained; this subject number will be used throughout the study.

Individuals who do not meet the eligibility criteria for participation in this study (i.e., screen failure) may be rescreened once. Rescreened subjects will be assigned a new screening number that is different from the number assigned at the initial screening.

9.2. SIG-001 Administration

9.2.1. Day -1

Patients will be admitted into the clinic on Day -1 (the day before the procedure) for baseline assessments and confirmation of eligibility. There is no Day 0 in this study. Patients are required to fast overnight or for at least 8 hours prior to SIG-001 administration.

9.2.2. Pre-Procedure Activities

Prior to laparoscopic administration of SIG-001, patients will be dosed with a bolus of plasma-derived or rFVIII (depending on the type of product the patient was receiving and hospital requirements), followed by maintenance FVIII administration either as repeat bolus administrations or as a continuous infusion, per Investigator's and/or site's standard clinical practice. The laparoscopic procedure will proceed ONLY if:

- a) pre-surgical FVIII activity levels reach ≥ 60 IU/dL (60% of normal) obtained within 1 hour of FVIII infusion
OR
- b) pre-surgical aPTT is normal AND measured pre- and post- dosing FVIII levels (IU/dL) reach a difference of at least 60% during PK assessment. This FVIII level difference may have been determined during prior screening visits, per the Investigator's judgment and preference.

PROTOCOL

Title: Safety and Efficacy of Encapsulated Allogeneic FVIII Cell Therapy in Haemophilia A
Study No. SIG-001-121

Prior to the laparoscopic procedure, patients will receive a single dose of one antibiotic (or a single dose of 2 different antibiotics), as per the site's standard clinical practice.

9.2.3. SIG-001 Procedure

These procedures should be carried out in the sterile field by trained study staff as described in the *Laparoscopic Procedure Manual*.

SIG-001 must be administered by a study surgeon who has been trained to the procedures for SIG-001 administration outlined in the *Laparoscopic Procedure Manual*. SIG-001 is placed into the greater sac of the peritoneal space via laparoscopy conducted under general anaesthesia. Each site will use their standard, clinically used laparoscopic methods and instrumentation to complete the surgery, supplemented with equipment, reagents, and IP provided by the Sponsor, including an 8mm trocar and a 24F catheter. Once in the peritoneal space, the catheter is inserted through a trocar, and syringes containing SIG-001 spheres and buffer at approximately 1:2 volume ratio are attached firmly to the catheter and the contents slowly expelled, including air volume. Once all syringes containing SIG-001 are administered, a syringe containing buffer alone will be administered to expel any remaining spheres from the catheter. Complete details regarding SIG-001 administration are provided in the *Laparoscopic Procedure Manual*.

9.2.4. Post-Procedure Activities

Following SIG-001 administration, patients will continue to receive FVIII to maintain trough levels $\geq 60\%$ for the first 48 hours after surgery. Patients may be discharged from the hospital on Day 3 or later per the Investigator's discretion.

FVIII dosing will be continued at home until the 1-week visit, to maintain minimal haemostatic trough levels of $\geq 30\%$ of FVIII activity. This post-procedure FVIII treatment regimen may involve twice daily dosing for standard half-life products or once daily dosing for extended half-life products. Patients may be discharged with a PICC line as needed. Per the Investigator's discretion, patients may remain in the hospital for longer observation during FVIII administration.

Patients will be withdrawn from FVIII therapy after the Week 1 (Day 7) visit, per the Investigator's discretion. If patients are not withdrawn from FVIII therapy at Week 1, the reason for continuing FVIII will be recorded.

9.3. Long Term Follow-up

Patients will be followed for approximately 5 years post SIG-001 administration for safety and efficacy per the Schedule of Assessments (Table 2 Schedule of Assessments).

FVIII levels will be measured at regular intervals throughout the study. Per the investigator's discretion, exogenous FVIII will be washed out for a minimum of 96 hours (4 days) and at least 168 hours (7 days) for prolonged half-life rFVIII products.

Throughout the study, all patients will have access to commercially available FVIII therapy, if needed, to treat bleeding episodes, for perioperative management of surgery or other medical procedures, or as preventative treatment prior to vigorous physical activity.

PROTOCOL

Title: Safety and Efficacy of Encapsulated Allogeneic FVIII Cell Therapy in Haemophilia A
Study No. SIG-001-121

9.4. Unscheduled Visits

Unscheduled visits may be necessary for safety monitoring or to repeat a study assessment. Information regarding concomitant medications and adverse events will be collected at all unscheduled visits. Data collected during an unscheduled visit will be captured in the EDC.

9.5. End-of-Trial Date

The End-of-Trial date will be based on the final data collection date for the entire study, which is the date of the last Follow-up call/visit.

10. STUDY ASSESSMENTS

Unless otherwise indicated, all study-specific assessments will be performed by the Investigator or designated study personnel. The procedures to be performed throughout the study are outlined in the Schedule of Assessments (Table 2 Schedule of Assessments). The sections below provide additional details regarding certain procedures and assessments listed in the Schedule of Assessments.

10.1. Safety Assessments

10.1.1. Medical History

A complete medical history will be collected at Screening. Information to be documented includes demographic information, prior and ongoing medical illnesses and conditions, and previous surgical procedures. Medical history related to the patient's diagnosis of haemophilia A will be documented, including FVIII therapies and transfusion and bleeding history in the 12 months prior to screening.

10.1.2. Physical Examination

Physical examinations will be performed in accordance with the Schedule of Assessments (Table 2 Schedule of Assessments).

At Screening, Day -1, and M60, a complete physical examination will be performed, which will include a review of general appearance (head, eyes, ears, nose, and throat), as well as the cardiovascular, dermatologic, gastrointestinal, genitourinary, lymphatic, musculoskeletal, neurologic and respiratory systems.

At all other clinic visits, a directed physical examination will be completed. The directed physical examination will be based on the patient's clinical status and will include general appearance, cardiovascular, gastrointestinal, neurologic, and respiratory assessments. Particular attention will be given to signs of bleeding as well as possible hemarthroses.

Clinically significant changes from baseline will be captured as AEs.

10.1.3. Target Joint Assessment

Target joints will be identified and assessed at Screening and yearly following SIG-001 administration. Target joints are defined as major joints (e.g. hip, elbow, wrist, shoulder, knee, ankle) into which repeated bleeding occurs and with symptoms of pre-existing target joint

PROTOCOL

Title: Safety and Efficacy of Encapsulated Allogeneic FVIII Cell Therapy in Haemophilia A
Study No. SIG-001-121

involvement (e.g., synovitis, persistent swelling, effusion, limitation of range of motion). Repeated bleeding is defined as a frequency of 3 or more bleeding episodes into the same joint in a consecutive 12-week period (Ota et al., 2007).

The modified HJHS scoring tool will be utilized for joint health assessment (Feldman et al., 2011). Six joints (left ankle-LA, right ankle-RA, left elbow-LE, right elbow-RE, left knee-LK, right knee-RK) will be scored on a scale from 0 to 20. Gait will be scored on a scale from 0 to 4. The total score will be the sum of scores from all 6 joints plus the gait score (range from 0 to 124), with 0 being normal and 124 representing most severe disease.

10.1.4. Vital Signs

Collection of vital signs will be performed in accordance with the Schedule of Assessments (Table 2 Schedule of Assessments). Vital sign measurements include temperature, respiratory rate, seated BP, and pulse. Seated BP measurements will be recorded after the patient has been sitting for at least 5 minutes. Three BP measurements will be recorded at Screening, and the average will be calculated for eligibility assessment. After screening, a single BP measurement will be sufficient.

10.1.5. Prior and Concomitant Medications

All concomitant medications will be collected from the time of informed consent until the patient's last study visit. Please refer to Section 7.5 for permitted, prohibited and prophylactic medications.

10.1.6. Height and Weight

Height will be collected at the Screening Visit only. Weight will be collected as specified in the Schedule of Assessments (Table 2 Schedule of Assessments).

10.1.7. Electrocardiogram

Resting 12-lead electrocardiogram (ECG) will be recorded as specified in the Schedule of Assessments (Table 2 Schedule of Assessments).

ECG assessments should be obtained after the patient has been in a supine position for at least 5 minutes and recorded while the patient remains in that position. ECGs should be performed before vital sign assessments and blood sample collections. If this is not possible, the ECG must be performed at least 10 minutes after blood draws.

Mean QT interval corrected for heart rate will be calculated using the QT interval corrected by Fridericia formulae (QTcF).

Any clinically significant abnormalities detected require confirmation with triplicate ECG.

Electrocardiogram findings will be reviewed by the Investigator and assessed as "Normal," "Abnormal, Not Clinically Significant," or "Abnormal, Clinically Significant" in the corresponding eCRF. Any clinically significant findings will be reported on the corresponding AE page in the eCRF.

10.1.8. Clinical Laboratory Tests

Routine laboratory tests for haematology, serum chemistry, coagulation and urinalysis will be

PROTOCOL

Title: Safety and Efficacy of Encapsulated Allogeneic FVIII Cell Therapy in Haemophilia A
Study No. SIG-001-121

performed at selected visits as specified in the Schedule of Assessments (Table 2 Schedule of Assessments). Additional clinical laboratory tests should be performed according to Investigator discretion as clinically indicated.

ABO blood typing, genotyping and screening for HIV, Hepatitis B, and Hepatitis C will be performed at the Screening visit.

Alcohol and illicit drug screening will take place at Screening.

At select timepoints (indicated in the Schedule of Assessments), additional blood samples will be collected and plasma and serum samples will be stored for exploratory future analyses. These analyses may include FVIII activity, SIG-001-specific inhibitor measurement, or other testing related to SIG-001. Additional details are included in the *Laboratory Manual*.

The Investigator (or designee) is responsible for reviewing available laboratory results for each patient to ensure that there are no laboratory abnormalities. Any out-of-range laboratory result that is considered clinically significant by the Investigator will be recorded as an AE and can be confirmed by repeat testing at the discretion of the Investigator. Clinically significant laboratory abnormalities at any visit will be followed to resolution (return to normal or to the baseline state) or until clinically stable as determined by the Investigator.

Instructions for obtaining and handling laboratory samples are provided in the *Laboratory Manual*.

A list of key clinical laboratory tests to be performed is presented in Table 4.

PROTOCOL

Title: Safety and Efficacy of Encapsulated Allogeneic FVIII Cell Therapy in Haemophilia A
Study No. SIG-001-121

**Table 4 Clinical Laboratory Tests**

HEMATOLOGY	BIOCHEMISTRY	URINALYSIS DIPSTICK	SEROLOGY	DRUG SCREEN
Erythrocytes	Sodium	pH & gravity	HBs Ag (Hepatitis B)	Alcohol
Haemoglobin	Potassium	Clarity & Colour	Anti-HBc (Hepatitis B)	Amphetamines
Haematocrit	Chloride	Protein	HBV DNA (Hepatitis B)	Barbiturates
Platelets (incl. MCV, MCH, MCHC)	Calcium	Glucose	HCV RNA (Hepatitis C)	Benzodiazepines
Leukocytes	Magnesium	Leukocytes	HIV Ag/Ab	Cocaine
Neutrophils	Bicarbonate	Bilirubin	HBe Ag	Methadone
Lymphocytes	Protein, total	Ketones	HIV RNA	Oxycodone
Monocytes	Albumin	URINALYSIS SEDIMENT	T- and B-cell profile	Propoxyphene
Eosinophils	Creatinine	RBC		THC
Basophils	Uric acid	WBCC		OTHER
Neutrophils (abs.)	Blood urea nitrogen	Casts		ABO blood typing
Lymphocytes (abs.)	ALT	Casts (comment)		F8 genotype
Monocytes (abs.)	AST	Crystals		VWF Ag
Eosinophils (abs.)	Alkaline phosphatase	Crystals (comment)		FVIII inhibitors
Basophils (abs.)	Bilirubin, direct	Bacteria		FVIII activity (one-stage & chromogenic assay)
	Bilirubin, total			
	LDH			
	Lipase			
	Creatine kinase			
	eGFR			
	GGT			
	Phosphorus			
	Glucose			
	Triglycerides			
	C-Reactive Protein			

PROTOCOL

Title: Safety and Efficacy of Encapsulated Allogeneic FVIII Cell Therapy in Haemophilia A
Study No. SIG-001-121

10.1.9. FVIII PK Assessment

FVIII PK assessment will be conducted prior to SIG-001 administration (i.e. during the screening period or on Day -1) to guide FVIII dosing during the perioperative period. For standard half-life FVIII products, PK sampling may include 2 to 3 timepoints, with samples at least 12 hours apart in a 48-hour period after factor infusion; particularly informative is the 24-hour sample. For extended half-life FVIII products, an additional sample at 60-84 hours after factor infusion is advisable. A trough level may be added only if the patient is to be infused with factor at the clinic (Iorio et al., 2017). The number and timing of samples are at the discretion of the Investigator. The actual collection times as well as FVIII administration time must be recorded. The assessment does not need to be conducted if previously completed and the information can be obtained from the medical records.

10.1.10. Patient Questionnaires

The following questionnaires will be administered at selected visits:

Quality-of-Life (Appendix 1)

The Haem-A-QoL Questionnaire is a haemophilia-specific quality-of-life assessment tool for patients who are 17 years old and above. It includes 46 questions pertaining to 10 dimensions of health-related quality-of-life (HRQoL) (Gringeri & Von Mackensen, 2008).

EQ-5D-5L (Appendix 2)

The EQ-5D-5L Questionnaire uses 5 questions to assess mobility, self-care, usual activities, pain/discomfort, and anxiety/depression. It is a standardized instrument that was established by the EuroQol Group, providing a single index value for health status (Rabin, Oemar, & Oppen).

Physical Activity Questionnaire (Appendix 3)

Changes in physical activity level will be assessed at selected visits by asking subjects to evaluate whether the frequency and/or the intensity of their activity level has increased, decreased or remained unchanged.

10.1.11. Magnetic Resonance Imaging (MRI)

To establish a baseline imaging record for each patient, a non-contrast upper and lower abdominal MRI will be performed during the Screening Period or on Day -1 as specified in the Schedule of Assessments (Table 2 Schedule of Assessments). If a patient is unable to undergo an MRI, an abdominal ultrasound will be done instead. A follow-up MRI is not required per protocol; however, it may be performed, if clinically indicated or if recommended by the Investigator. Repeat imaging will be included in the study record.

10.2. Efficacy Assessments

Efficacy assessments will include serial measurement of FVIII activity. This activity will be assessed using both a one-stage clotting assay and a chromogenic substrate assay.

PROTOCOL

Title: Safety and Efficacy of Encapsulated Allogeneic FVIII Cell Therapy in Haemophilia A
Study No. SIG-001-121

10.2.1. FVIII Activity

Throughout the study, FVIII activity levels will be assessed by one-stage and chromogenic assays performed by the central laboratory from samples obtained at regular intervals. Per the Investigator's discretion, exogenous FVIII use will be washed out for a minimum of 96 hours (4 days for standard half-life FVIII products) and at least 168 hours (7 days for prolonged half-life rFVIII products) to ensure that only FVIII secreted by SIG-001 is measured.

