6.4. Dose Escalation Design

Patients will be enrolled in one of 3 escalating dose cohorts. Dosing will be staggered by at least 8 weeks for the first 3 patients enrolled in the study. Thereafter, doses will be staggered by at least 4 weeks for the remaining patients in each dose cohort and between dose cohorts. Cohort expansion does not require staggered enrolment. Following SIG-001 administration, safety and efficacy parameters (FVIII activity) through at least the Week 8 visit (first 3 patients) and at least the Week 4 visit (for the remaining patients in any dose cohort and between dose cohorts) will be reviewed by the Safety Review Committee (SRC) prior to dosing any additional patients (Section 11.1).

Decisions regarding dose escalation will be made by the SRC based on review of safety and FVIII activity data of the preceding patient(s) and/or cohort(s) and the Dose Escalation Decision Tree (Figure 3). Dose escalation will occur only if no dose-limiting toxicities (DLTs) and/or clinically-relevant safety issues have been noted. FVIII activity will be reviewed to inform the dose selection (volume of spheres) for the next cohort.

After the first dose (Dose 1, CCI of SIG-001 spheres), the dose may be increased (e.g. planned Dose 2 & 3) or decreased/de-escalated (Dose -1). No dose increase will be >2-fold higher than a dose level previously found to be safe, and no dose will exceed the maximum dose of CCI.

If any patient achieves FVIII activity >100 IU/dL (equivalent to >100% normal FVIII activity) no further dose escalation will occur. Dosing may proceed at the same level or at a lower level.

PROTOCOL

Title: Safety and Efficacy of Encapsulated Allogeneic FVIII Cell Therapy in Haemophilia A
Study No. SIG-001-121

Cohort 1, Dose 1

If the starting dose in the first patient in Cohort 1, Dose 1 is safe and tolerated and FVIII activity is ≥ 5 IU/dL (equivalent to $\geq 5\%$ normal FVIII activity) at Week 8, the next 2 patients will be administered the same dose and followed for safety and efficacy per the Schedule of Assessments (Table 2 Schedule of Assessments). SIG-001 administration for Patients 2 and 3 will be staggered to include a safety review at least 8 weeks after SIG-001 administration.

If no DLTs or clinically-relevant safety issues occur following safety review of Patient 1 Cohort 1 data but FVIII activity in Patient 1 Cohort 1 is <5 IU/dL at Week 8, dose escalation may occur, and the study will progress to Cohort 2, Dose 2.

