Doses will be staggered by at least 8 weeks for the first 3 patients enrolled in the study. Thereafter, doses will be staggered by at least 4 weeks for the remaining patients in any dose cohort and between dose cohorts.

Cohort 2, Dose 2

If the starting dose in the first patient in Cohort 2, Dose 2 is safe and tolerated, the next 2 patients will be administered the same dose via a staggered approach with a safety review after SIG-001 administration, i.e. Dose 2, if:

- 1) FVIII activity in Cohort 2 Patient 1 is ≥ 5 IU/dL, or
- 2) FVIII activity in Cohort 2 Patient 1 is <5 IU/dL but FVIII activity in Cohort 1 Patient 2 or Cohort 1 Patient 3 is ≥ 5 IU/dL

The study will proceed to the highest dose, i.e. Cohort 3, Dose 3, if no DLT or clinically-relevant safety issues occur and:

- 1) FVIII activity in Cohort 1 Patient 1 is <5 IU/dL and FVIII activity in Cohort 2 Patient 1 is also <5 IU/dL, or
- 2) FVIII activity in Cohort 2 Patient 1 is <5 IU/dL, and FVIII activity in Cohort 1 Patients 2 and Patient 3 is <5 IU/dL.

PROTOCOL

Title: Safety and Efficacy of Encapsulated Allogeneic FVIII Cell Therapy in Haemophilia A
Study No. SIG-001-121

Cohort 3, Dose 3

If the starting dose in the first patient in Cohort 3, Dose 3 is safe and tolerated and no DLT or clinically-relevant safety issues occur, the next 2 patients will be administered the same dose via a staggered approach with a safety review after SIG-001 administration, i.e. Dose 3, if:

- 1) FVIII activity in Cohort 3 Patient 1 is ≥ 5 IU/dL, or
- 2) FVIII activity in Cohort 3 Patient 1 is < 5 IU/dL but FVIII activity in Cohort 2 Patient 2 or Cohort 2 Patient 3 is ≥ 5 IU/dL.

[figure not shown]
If FVIII activity in Cohort 3 Patient 1 is < 5 IU/dL and all prior patients had FVIII activity < 5 IU/dL, no further patients will be dosed and enrolment will be stopped. This dose escalation algorithm is intended to monitor patient safety while minimizing patient exposure to subtherapeutic SIG-001 doses. Cohort expansions (up to 3 additional patients) can be initiated after one dose cohort has completed at least 8 weeks of follow-up or after all dose cohorts have completed at least 4 weeks of follow-up. Cohort expansion may be triggered in order to collect additional information regarding safety and efficacy. Decisions regarding cohort expansions will be made by the SRC.

PROTOCOL

Title: Safety and Efficacy of Encapsulated Allogeneic FVIII Cell Therapy in Haemophilia A
Study No. SIG-001-121

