7.3. Inclusion Criteria

Patients must meet all inclusion criteria to be eligible for participation in the study:

1. Males aged 18 years or older
2. Diagnosis of Haemophilia A as follows:
 - a) Severe ($< 1\%$ FVIII activity) receiving FVIII prophylaxis or on-demand treatment; or
 - b) Moderately-severe ($\geq 1\% - \leq 2\%$ FVIII activity) receiving FVIII prophylaxis
3. Greater than 150 exposure days to treatment with FVIII products
4. Fertile males (not surgically sterilized) who have sexual partners that are women of childbearing potential must be willing to use a barrier method of contraception (e.g. condoms) for at least 90 days post-SIG-001 administration
5. Normal levels of VWF antigen (≥ 50 IU/dL)

PROTOCOL

Title: Safety and Efficacy of Encapsulated Allogeneic FVIII Cell Therapy in Haemophilia A
Study No. SIG-001-121

6. Able and willing to provide informed consent
7. Willing to withdraw from FVIII prophylaxis during specified periods in the study

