13.5.2. Factor VIII Activity Levels

Factor VIII activity (as measured by one-stage and chromogenic assays) will be summarized separately using summary statistics for each scheduled assessment, by dose cohort and overall. Factor VIII activity will be correlated to SIG-001 dose received.

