13.6.2. Other Safety Assessments

For the absolute values and change from baseline summaries, for vital signs, laboratory data, and ECGs, the baseline value will be the latest result obtained prior to the start of study product. Standardized units will be calculated. The QTcF will be derived during creation of the reporting database using the reported ECG values (RR and QT) using Fridericia's formula:

$$\text{Where, } \text{QTcF} = \text{QT/RR}^{(1/3)} \text{ where RR is in seconds.}$$

Summaries will be by dose cohort and overall.

Corrected calcium will be derived during creation of the reporting database using the following formula: Corrected calcium (mmol/L) = total calcium (mmol/L) + ([40 – albumin (G / L)] x 0.02).

Laboratory toxicity data will be coded to CTCAE v5.0, where applicable, and summarized by shift tables of worst toxicity grade post-baseline compared with baseline toxicity grade.

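### The washout cannot leave only SIG-001 FVIII in patients who keep 1-2 IU/dL of their own, and the raw summary credits that amount to the product.

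*Protocol*

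**What the plan says.** Section 10.2.1 of the protocol has exogenous FVIII washed out before sampling, at the investigator's discretion, for at least 96 hours (standard half-life products) or 168 hours (prolonged half-life products). The stated purpose is "to ensure that only FVIII secreted by SIG-001 is measured". The synopsis, in its summary of patient procedures, says the same.

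Section 7.3 admits two groups. Inclusion 2a reads "Severe ($< 1\%$ FVIII activity) receiving FVIII prophylaxis or on-demand treatment"; inclusion 2b reads "Moderately-severe ($\geq 1\% - \leq 2\%$ FVIII activity) receiving FVIII prophylaxis".

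Two parts of the protocol use the measured level:

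- Section 13.5.2: one-stage and chromogenic results "will be summarized separately using summary statistics for each scheduled assessment, by dose cohort and overall". Activity is also to be correlated with the dose received. No adjustment for the patient's own level is mentioned.
- Section 6.4: the level is compared with 5 IU/dL. For the first patient, if no safety issue arises but "FVIII activity in Patient 1 Cohort 1 is <5 IU/dL at Week 8, dose escalation may occur". The Cohort 2 and Cohort 3 rules and the rule that ends enrolment use the same cut-off, also without reference to a baseline.

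**The concern.** A washout of infused product does nothing to FVIII that the patient makes. For a 2b patient the sample therefore contains endogenous plus SIG-001 FVIII, and the property claimed in section 10.2.1 fails for a group that the protocol deliberately admits.

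Two things depend on that property. The first is the dose-activity description, a secondary objective. With up to three patients per initial cohort and no randomisation, the mix of 2a and 2b patients can differ between cohorts, and part of an apparent dose difference could reflect who was enrolled. The second is the meaning of the 5 IU/dL level. If a reader takes section 10.2.1 at its word, that level is SIG-001 output; as measured, it is total activity. The first Cohort 1 decision rests on one patient, so the difference in meaning is not averaged out.

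**Working it through.** The protocol gives no figure for this point, so there is none to reproduce. The check is additive.

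**Inputs**

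- Endogenous level E: 1 to 2 IU/dL under inclusion 2b, below 1 IU/dL under 2a (section 7.3; 1% of normal = 1 IU/dL).
- Cut-off: 5 IU/dL (section 6.4).
- Target for Dose 1: 0.10 IU/mL × 100 = 10 IU/dL; predicted range 6-22% (section 6.5.1, Table 3).
- Initial cohort size: up to 3 (section 6.3).

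**Model.** After complete washout, measured level M = S + E, where S is the SIG-001 contribution.

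**1. Effect on the summaries in 13.5.2.** One 2b patient with E = 2 moves a three-patient mean by 2/3 = 0.67 IU/dL; with E = 1, by 1/3 = 0.33. Three such patients with E = 2 move it by 2. Relative to the modelled activity:

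| E (IU/dL) | Share of 10 IU/dL target | Relative to 6 (low end, Dose 1) | Relative to 22 (high end, Dose 1) |
|---|---|---|---|
| 1 | 1/10 = 10% | 1/6 = 17% | 1/22 = 5% |
| 2 | 2/10 = 20% | 2/6 = 33% | 2/22 = 9% |

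**2. Effect at the 5 IU/dL level, if that level is meant as S.** M ≥ 5 requires S ≥ 5 − E.

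- E = 1: S ≥ 4, and 1/5 = 20% of the cut-off is endogenous.
- E = 2: S ≥ 3, and 2/5 = 40% is endogenous.
- Severe patient (E below 1): S between just over 4 and 5.

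The two meanings give different answers only when 5 − E ≤ S < 5, that is from 4 (E = 1) or 3 (E = 2) to just under 5 IU/dL. The whole Dose 1 prediction of 6-22% lies above this window, so it is reached only if the product delivers less than modelled.

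**3. Illustration, on assumed variability.** The protocol gives no between-patient variation. Suppose S is lognormal with a coefficient of variation of 50%, so σ = √ln(1 + 0.5²), and P(M ≥ 5) = 1 − Φ([ln(5 − E) − ln(median)]/σ):

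| Median S (IU/dL) | E = 0 | E = 1 | E = 2 |
|---|---|---|---|
| 3 | 0.14 | 0.27 | 0.50 |
| 4 | 0.32 | 0.50 | 0.73 |
| 10 (the target) | 0.93 | 0.97 | 0.995 |

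Endogenous FVIII matters when the product under-delivers and hardly at all when it performs as modelled.

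**4. Is E available?** Table 2 has a Screening FVIII sample, but nothing ties it to a washout, and 2b patients must be on prophylaxis to enter. Section 13.6.2 says "the baseline value will be the latest result obtained prior to the start of study product", but this is written for vital signs, laboratory data and ECGs. If it were applied to FVIII, the latest pre-product value could be the Day 1 local sample, taken around a bolus meant to bring the level to at least 60 IU/dL (section 9.2.2).

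**The case against.** The strongest reply is that total activity is what the protocol means to study. The objective and endpoint are FVIII activity levels after administration, not activity attributable to SIG-001, and section 13.5.2 summarises exactly that. Section 6.5.2 ties benefit to circulating activity above 12%, and section 6.4 expresses 5 IU/dL as a percentage of normal and aims to avoid subtherapeutic doses. Detailed methods are left to the SAP, which may add a baseline-corrected summary. The Safety Review Committee includes site investigators, who can know each patient's severity, and escalation after a low first result is permitted, not required.

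Much of this stands. A reader might infer that the 5 IU/dL rule is biased upward. The documents do not show that: it can be read as a total-level criterion, and then nothing is inflated. The opposite reading is also open, because the dose model in section 6.5.1 is built from sphere secretion and bioavailability and section 10.2.1 says that only SIG-001 FVIII is measured. The protocol does not choose between them.

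A reader might also infer that the endogenous amount is known and already measured, so that correction is mere subtraction. That is not supported either: the Screening sample may contain infused product, and subtracting it would understate SIG-001.

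The reply does not rescue the washout sentence. A SAP cannot correct a protocol statement, or settle what a level fixed in the protocol refers to.

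**Conclusion.** The statement in section 10.2.1 and the synopsis is wrong for inclusion-2b patients. As a result, the raw summary and dose correlation in section 13.5.2 credit SIG-001 with up to 2 IU/dL per such patient. Severe patients add less than 1 IU/dL each.

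The effect on dose decisions is conditional. It exists only if 5 IU/dL is meant as SIG-001 output, a 2b patient is decisive, and SIG-001 supplies 3 or 4 to just under 5 IU/dL. The number of 2b patients is not fixed and may be zero. The size assumes that endogenous and SIG-001 activity add, that the assays do not separate them (the protocol claims no such thing), and that washout of infused product is complete. The point is modest in size, but it concerns what a secondary endpoint measures and is cheap to put right.

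**What to change.** 1. In section 10.2.1 and the synopsis, say that total FVIII (endogenous plus SIG-001) is measured after infused product has been washed out.
2. In section 13.5.2, keep the raw summary and place beside it a summary of FVIII activity minus the patient's own pre-treatment endogenous level. Use the Screening sample only if it was washed out, otherwise the documented historical baseline, and record source and assay. Do not use any sample containing infused FVIII, which rules out a Day 1 value taken after the bolus.
3. Reconcile sections 10.2.1, 7.3 and 6.4 by stating whether the 5 IU/dL level means total or SIG-001-attributable activity. This asks for a definition only; it proposes no change to the threshold or the dose rule.

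The cost is two wording changes, one derived variable and a recorded baseline source. The downside is that for patients on prophylaxis the baseline may be historical and from a different assay, so the subtracted summary is approximate and should be labelled so.
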